Official Title: Role of Levothyroxine Supplementation in Delayed Recovery Following Cardiac Surgery

NCT Number: NCT06660823

Document Date: November 1, 2024

Protocol Of A Paper For Partial Fulfilment Of Research In Anesthesia, ICU and pain management

The title: Role of Levothyroxine supplementation in delayed recovery following cardiac surgery.

NAME OF RESEARCHER: [name]

Academic Position: lecturer of Anaesthesia, Intensive Care and Pain management

Department: Faculty of Medicine-Ain Shams University

NAME OF RESEARCHER: [name]

Academic Position: Lecturer of Anaesthesia, Intensive Care and Pain management

Department: Faculty of Medicine-Ain Shams University

**Faculty of Medicine
Ain Shams University
2024**

1. INTRODUCTION/ REVIEW (Maximum 1000 words) *“References are needed”*

Research indicates that hypothyroidism decreases heart contractility, reduces stroke volume and rate, affects the vascular endothelium, and increases the risk of atherosclerosis, systemic vascular resistance, hypertension [1], atherogenic lipid profile, and coagulation abnormality [2].

Hypothyroidism was reported to be strongly related to cardiovascular disease, respiratory complications, neurological complications, and a significant difference in ventilator weaning time [3].

Severe thyroid dysfunction is related to muscle relaxation and lead to respiratory muscle depression and disturbed conscious level.[3]

Surgical stress of cardiac surgery might be followed by a prolonged recovery process and cardiac dysfunction [3].

The exact physiology of thyroid disease and the relationship with post cardiac surgery remain unclear. Thus far, large-scale clinical statistical analysis evidence on the complication rate and long-term mortality is lacking. Current important prognostic assessment tools such as EuroSCORE II [4], and Society of Thoracic Surgeons (STS) score [5] do not include thyroid function assessment, even though it has a significant impact on the metabolic, cardiovascular, and circulation system.

2. AIM/ OBJECTIVES (Maximum 300 words)

The primary aim of this study is to investigate the effect of supplementation of oral levothyroxine in delayed recovery patients post cardiac surgery.

3. METHODOLOGY:

Patients and Methods/ Subjects and Methods/ Material and Methods (Maximum 1000 words) "References may be needed"

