Premedication will be given according to standard protocol in cardiac anesthesia. Routine monitoring included a five-lead electrocardiogram, pulse oximeter and invasive blood pressure. Anesthesia will be induced with midazolam 0.02mg/kg and fentanyl 2-5 microgram /kg and muscle relaxation were achieved cisatracurium 0.15 mg/kg intravenous. After tracheal intubation, central venous line and TEE inserted, then anesthesia will be maintained throughout the procedure with morphin20 microgram/kg /min, cisatracurium 2mg/kg/min and sevoflurane 2%. Ventilation will be adjusted to maintain end-tidal carbon dioxide in the range of 30-40 mmHg.

On ICU arrival all patients will be subjected to standardized management as per institutional protocols. Patients who show signs of delayed recovery defined as either prolonged ventilation for 48 hours or delayed conscious level recovery for 48 hours despite exclusion of muscle relaxants and/or sedative drugs. Those patients will undergo CT brain, CT chest and neurological examination to exclude structural damage as per institutional protocols. Also, metabolic profile screening including full kidney function, full liver function, electrolyte and thyroid profile (TSH, free T3, free T4) to exclude correctable metabolic abnormalities.

Patients then divided into two groups: group A will receive levothyroxine via Ryle, dose of 25 to 50 ug/ day according to BMI, while group B will receive placebo in form of inert starch tablet.

Daily assessment of conscious level according to Glasgow Coma Scale (GCS) and spontaneous breathing trial by ICU consultant till ICU discharge.

Assessment of thyroid profile (free T3, free T4, TSH) before hospital discharge.

Endpoints of the study:

Primary end point:

1. Improvement of Glasgow coma scale and spontaneous breathing trial before ICU discharge.

Secondary end points:

1. Total ventilation time.
2. Total ICU stay.
3. Total hospital stay.
4. Total amount of inotropic support.
5. Improvement of cardiac function by echocardiography.

Ethical considerations:

The study protocol will receive ethical approval from the Research Ethical Committee, Faculty of Medicine Ain Shams University.

Informed consent will be obtained from each patient before patients' allocation.

Sample Size Calculation

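### No listed endpoint counts death or adverse events, and no rule says how a death enters the duration analyses, so a mortality difference could distort those results in either direction

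*Combined protocol and SAP*

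**What the plan says.** Under Endpoints of the study, the primary endpoint is "Improvement of Glasgow coma scale and spontaneous breathing trial before ICU discharge". The list headed "Secondary end points" then holds "Total ventilation time", "Total ICU stay", "Total hospital stay", "Total amount of inotropic support" and "Improvement of cardiac function by echocardiography". The numbered list is intact, and the documents have no adverse-event section. Mortality appears only in the Introduction, as a gap in the evidence, and in the title of a reference.

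Conscious level and breathing trials are assessed daily until ICU discharge. The last planned assessment is a thyroid profile before hospital discharge. No follow-up of vital status is described.

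The Statistical Analysis section commits to intention to treat, two-tailed tests, and a t-test or Mann-Whitney test for continuous variables. It fits a mixed model to the GCS trajectory and plans Kaplan-Meier and Cox analyses for time-to-event outcomes. It does not name those events, their time origin or their censoring. It gives no rule for a patient who dies.

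**The concern.** The population makes deaths plausible: patients aged 45 to 70 after on-pump open-heart surgery, urgent and emergency cases included, who are still ventilated or not awake at 48 hours. The Introduction says of thyroid function that "it has a significant impact on the metabolic, cardiovascular, and circulation system". That sentence is about risk scores that leave thyroid function out and does not say levothyroxine causes harm, but it is a reason to count cardiac events by arm.

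Two things are at stake. First, the plan compares no harm events between arms, so net benefit cannot be judged. Second, a shorter ventilation time, shorter stay or lower inotrope total may mean recovery or may mean death. A longer one may mean slow recovery, or deaths after a long supported course. Nothing in the plan requires reporting the deaths that would let a reader tell these apart.

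**Working it through.** **1. The plan's own figure.** Sample Size Calculation: effect size 0.80 in GCS change, two-sided alpha 0.05, power 80%. n per arm = 2(1.960 + 0.842)² / 0.80² = 2 × 7.85 / 0.64 = 24.5, so 25. The figure reproduces. It concerns GCS only and is not affected by this point.

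**2. What a death does to each endpoint.**

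| Endpoint | Counts deaths or adverse events? | Effect of a death |
|---|---|---|
| GCS and breathing trial | No | Series ends; no rule |
| Ventilation time | No | Total stops |
| ICU stay | No | Total stops |
| Hospital stay | No | Total stops |
| Inotrope total | No | Total stops |
| Echocardiography | No | Missing |

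None of the six counts deaths or adverse events; four of the five secondaries are cut short.

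**3. Size and direction for mean stay.** Let a proportion p of an arm die, with mean stay D for those who die and S for survivors, counted from allocation. The arm mean is (1 − p)S + pD. With no effect on recovery, treated minus control = (p_T − p_C)(D − S). The sign depends only on whether those who die stay shorter or longer than survivors. All rates and durations below are assumptions.

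- Early deaths, S = 12 and D = 4 days. For 10% vs 20%: 0.10 × (4 − 12) = −0.8 days. For 10% vs 30%: 0.20 × (−8) = −1.6 days.
- Deaths after long stays. Survivors log-normal, median 10 days and log-SD 0.5, so mean 10 × exp(0.125) = 11.33. Deaths with median 20 days and the same log-SD, so mean 22.66. For 10% vs 20%: 0.10 × 11.33 = +1.1 days. For 10% vs 30%: 0.20 × 11.33 = +2.3 days.

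**4. Effect on the planned test.** Simulation with 35 per arm, 20,000 trials per row, two-sided Mann-Whitney test at 0.05 and no effect on recovery. Survivors are log-normal as above. Early deaths are exponential with mean 4 days, capped at the stay the patient would otherwise have had. Late deaths are as in step 3.

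| Deaths, control vs treated | Timing | Mean difference (days) | Significant for treatment | Significant against |
|---|---|---|---|---|
| 10% vs 10% | early | 0.0 | 2.5% | 2.4% |
| 10% vs 20% | early | −0.8 | 8.7% | 0.5% |
| 10% vs 30% | early | −1.6 | 22.3% | 0.1% |
| 10% vs 20% | late | +1.1 | 0.7% | 6.8% |
| 10% vs 30% | late | +2.3 | 0.2% | 15.8% |

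**5. The time-to-event models.** If the event is leaving the ICU or hospital for any reason, a death counts as an early success. If death is censored, it does not shorten the duration, but the dead are treated as patients who could still be discharged later. If the event is survival, the plan does not list it as an endpoint. The text does not say which applies.

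**6. What 35 per arm can say about deaths.** With 0/35 events, the exact upper 95% limit is 1 − 0.025^(1/35) = 10.0%. Power for 10% vs 20% is about 21%; 80% power would need 199 per arm.

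**The case against.** The strongest case on the other side has four parts.

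- **Every listed endpoint can move against treatment.** Tests are two-tailed. A drug that worsened circulation in survivors could raise inotrope use, ventilation time and stay, and could lower GCS or echocardiographic function. This stands. A reader might infer that the endpoint set can only point toward benefit; the documents do not support that.
- **Some planned measurements bear on safety.** These are the thyroid profile before discharge, daily GCS and breathing trials, inotrope total and echocardiography. This also stands, so it would be wrong to infer that safety goes wholly unassessed by arm. But these are not event counts, and echocardiography is framed only as improvement.
- **The Kaplan-Meier and Cox analyses might cover survival, or might censor deaths.** They might, but no event is named and no death endpoint is defined. Intention to treat does not settle it either: it fixes who is analysed, not what value a dead patient contributes.
- **Early death is only one pattern.** Patients qualify only after 48 hours of delayed recovery, so long supported courses before death are plausible, and the sign then reverses. This stands, and is why both directions are shown. The mortality rates are assumed; even with early deaths at 10% vs 20%, a significant false benefit appears in 8.7% of simulated trials, not in most of them.

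**Conclusion.** The concern holds as a gap in the endpoint list and in the handling of death. It does not show a bias toward benefit. If mortality differs between arms, the four cumulative secondaries cannot be interpreted as they stand: the shift in mean stay is about −0.8 to −1.6 days with early deaths, or +1.1 to +2.3 days with deaths after long stays, for 10% vs 20% and 10% vs 30%. These sizes rest on assumed death rates and durations, stay counted from allocation, and no effect on recovery. With equal mortality and timing the between-arm shift disappears, but the plan does not require the data that would show this. The GCS trajectory has a related gap, since it also ends at death without a rule. The primary analysis can still be run, so this is a change that should be made rather than one without which the trial fails.

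**What to change.** Add to the endpoint list, counted from allocation:

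- all-cause death to hospital discharge and at one fixed horizon;
- adverse events, including cardiac events and events leading to stopping study drug.

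Report each by arm as n/N with a risk difference and exact 95% CI, without a significance claim.

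In the Statistical Analysis section, state how death enters each analysis, so that dying is never the favourable result. Two options are ventilator-free days with death scored worst, or death as a competing event in time-to-event models whose event and time origin are named. Show deaths beside each duration result and beside the GCS result. That display alone would not be enough, because the durations would remain truncated.

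The cost is a paragraph of text, a short form filled from routine ICU records, vital status at the fixed horizon, and imprecise estimates at 35 per arm. The Sample Size Calculation describes enrolment in the past tense. If it is complete, the new outcomes must be taken from charts and labelled as added later; events that were not charted may be lost.

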This study is a prospective, randomized controlled trial that will study the postoperative clinical outcomes of levothyroxine supplementation in delayed recovery or prolonged ventilation patients post cardiac surgery.

Randomization will be performed using a computer-generated randomization sequence and allocation concealment to be maintained all through the time of procedure, by using opaque, numbered, and sealed envelopes.

The study protocol will receive ethical approval from the Research Ethical Committee/ Institutional Review Boards, Faculty of Medicine Ain Shams University.

Informed consent will be obtained from each patient before patients' allocation.

Type of the study: prospective randomized clinical trial study protocol.

Study Setting: The operating theaters and ICU of Cardiothoracic institute of Ain Shams University Hospitals.

Study period: one year.

Sample Size:

Using PASS 15 program for sample size calculation, setting power at 80% and alpha error at 0.05, it is estimated that sample size of 25 patients per group total 50 patients can detect an effect size .80 or the difference between two groups regarding different qualitative outcome measures using two-sized a z test

Study population:

Inclusion criteria:

- Age group: Adult patients from age of 45 to 70 years.

Hypothyroidism was reported to be strongly related to cardiovascular disease, respiratory complications, neurological complications, and a significant difference in ventilator weaning time [3].

- Sex: Both sexes
- Elective, urgent and emergency open heart surgeries.

Exclusion criteria:

- Patients refuse to give informed consent.
- Patient younger than 45 years old, older than 70 years old.

- Off pump patients.
- Patients known hypothyroidism on levothyroxine supplementation.
- Patients known hyperthyroidism on Carbimazole.

Sampling method:

Patients will be randomly allocated by computer generated randomization into two groups A and B:

- **Group A (Study group):** patients receiving oral supplementation of levothyroxine.
- **Group B (Control):** patients receiving Placebo drug.

Anesthetic management:

Full standard preoperative assessment for cardiac surgery will be done for all patients included in the study before planned procedures.

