Using PASS 15.0 (NCSS LLC), detecting an effect size of 0.80 in GCS change ($\alpha = 0.05$, power = 80%) required 25 patients per arm. To ensure adequate power for secondary endpoints and allow for dropouts, we enrolled 35 patients per group (total $n = 70$).

Statistical Analysis

Analyses adhered to the intention-to-treat principle. Continuous variables are reported as mean \pm SD or median (IQR) and compared using Student's t-test or Mann-Whitney U test, as appropriate. Categorical variables are expressed as counts (%) and compared by χ^2 or Fisher's exact test.

- **Primary analysis:** Linear mixed-effects regression modeled GCS trajectories over time, with group, time, and their interaction as fixed effects and patient as a random effect.
- **Time-to-event outcomes:** Kaplan-Meier curves and Cox proportional hazards models yielded hazard ratios (HRs) and 95% confidence intervals (CIs).
- **Mediation:** The Sobel test quantified the proportion of EF preservation attributable to changes in free T3.

- **Sensitivity and subgroup analyses:** Inverse probability weighting assessed robustness; prespecified subgroups included diabetes status and CPB duration > 200 minutes.

All tests were two-tailed with $\alpha < 0.05$. Statistical analyses were performed using R v4.3.1 with the lme4, lavaan, and survminer packages.

4. REFERENCES (Maximum 20 references)

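### The echocardiographic improvement endpoint presupposes a starting value, but no stated analysis adjusts for it, which gives up some precision

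*Combined protocol and SAP*

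**What the plan says.** Section 3 (Methodology), under the secondary end points, lists as item 5 "Improvement of cardiac function by echocardiography". It names no echocardiographic parameter, baseline scan, follow-up time or threshold for improvement.

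The Statistical Analysis section gives two general rules for comparing arms. Continuous variables are "compared using Student's t-test or Mann-Whitney U test, as appropriate". For the rest, "Categorical variables are expressed as counts (%) and compared by χ^2 or Fisher's exact test". Neither rule includes a covariate.

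Three other items in that section might bear on EF:

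- Mediation, the only place where EF is named: "The Sobel test quantified the proportion of EF preservation attributable to changes in free T3". No covariates are listed.
- The longitudinal model, which is for the Glasgow Coma Scale (GCS) only: "Linear mixed-effects regression modeled GCS trajectories over time, with group, time, and their interaction as fixed effects".
- Sensitivity analysis: "Inverse probability weighting assessed robustness". Neither the outcome nor the weighting covariates are given.

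**The concern.** Improvement and preservation both compare a later value with an earlier one, so scoring this endpoint requires a starting EF for each patient. Having collected it, the plan does not say that it will be used as a covariate. Under the general rules, the arms would be compared on change in EF, on follow-up EF alone, or on a yes/no version of improvement.

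Testing change fixes the slope on the starting value at 1; testing follow-up alone fixes it at 0. Regression of follow-up on group and starting value (ANCOVA) estimates the slope, and in large samples its variance is no greater than that of either alternative.

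What is at stake is power for one secondary endpoint and for the mediation analysis built on it, and how far the result moves with a chance difference in starting EF. The Sample Size Calculation section gives power for secondary endpoints as one reason for going from 25 to 35 per arm, so a gain that needs no further patients serves the plan's own aim.

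**Working it through.** **The plan's own figure.** The inputs are an effect size of 0.80 for GCS change (Sample Size Calculation), "setting power at 80% and alpha error at 0.05" (Section 3, Sample Size) and "All tests were two-tailed" (Statistical Analysis). The normal approximation gives n per arm = 2 × ((1.960 + 0.842)/0.80)² = 24.53, rounded up to 25. This matches the plan (the t-based value is 25.52, so 26). It is sized on GCS and says nothing about EF.

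**Inputs for EF.** The 35 per arm comes from the Sample Size Calculation section. The documents give neither an SD for EF, nor an EF effect size, nor a correlation ρ between starting and follow-up EF. I assume equal SDs at both times, a true difference of 0.5 SD, ρ from 0.3 to 0.8, and both scans available in all 35 patients per arm.

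**Variance of the comparison**, relative to follow-up EF alone:

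- follow-up alone: 1
- change: 2(1 − ρ)
- ANCOVA: 1 − ρ²

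The ratio of ANCOVA to change is therefore (1 + ρ)/2.

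**Power** at 35 per arm, two-sided 0.05, two-sample t with standardised difference 0.5/√(variance factor):

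| ρ | Variance: change | Variance: ANCOVA | Power: follow-up alone | Power: change | Power: ANCOVA | Gain over better unadjusted option |
|---|---|---|---|---|---|---|
| 0.3 | 1.40 | 0.91 | 54% | 41% | 58% | 4 points |
| 0.5 | 1.00 | 0.75 | 54% | 54% | 66% | 12 points |
| 0.7 | 0.60 | 0.51 | 54% | 76% | 82% | 6 points |
| 0.8 | 0.40 | 0.36 | 54% | 90% | 93% | 3 points |

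The gain peaks at ρ = 0.5 because change and follow-up alone tie there. Against follow-up alone, the variance saving runs from 9% (ρ = 0.3) to 64% (ρ = 0.8). Against change, it runs from 35% down to 10%.

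**Small-sample cost.** With 70 patients, estimating the slope multiplies the expected ANCOVA variance by about 67/66, or 1.5%. ANCOVA then loses to follow-up alone only if (1 − ρ²) × 67/66 > 1, that is ρ < √(1/67) = 0.12.

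**Chance imbalance.** The standard error of the difference in mean starting EF is √(2/35) = 0.24 SD.

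**The case against.** The strongest reply is that the premise is partly inferred. The endpoint line names no parameter; EF comes from the mediation bullet. Nothing explicitly sends this endpoint to the t-test or Mann-Whitney rule, and if improvement is scored yes/no the power figures above do not apply. This stands, and it limits the claim: every rule that could apply is unadjusted, but which one will be used is not stated.

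A reader might go further and infer that EF has no regression model at all. The documents do not support that. A Sobel test of EF through free T3 implies an outcome equation for EF; the gap is that its covariates are not listed. The inverse probability weighting might include starting EF, but nothing says so, and it is only a sensitivity analysis.

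A reader might also infer bias, because regression to the mean flatters the arm that starts lower when change is tested. That holds only conditional on an observed imbalance. Over randomisations the unadjusted comparison is unbiased.

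Two readings of the size should be resisted. The 12-point gain is the most favourable case, not a typical one. And 0.80 is the plan's effect size for GCS change, so it is not a planned effect for EF.

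Finally, no baseline echocardiogram is scheduled; the anaesthetic section mentions only intraoperative TEE, which precedes allocation at 48 hours or later. A pre-treatment scan may therefore need to be specified, although improvement cannot be scored without some starting value. The Statistical Analysis is written in the past tense, but that alone does not show that outcome data had been examined.

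**Conclusion.** The point holds as a minor matter of precision and specification. The endpoint depends on a starting value, every between-arm rule that could apply ignores it as a covariate, and none is named for the mediation model's EF equation. If EF is analysed as continuous with 35 per arm and a true difference of 0.5 SD, adjustment adds about 3 to 12 points of power over the better unadjusted choice for correlations of 0.3 to 0.8. The benefit is larger if the weaker unadjusted option would have been used; the plan does not say which would be. Both the correlation and the EF difference are assumptions. No bias is shown.

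**What to change.** Add to the Statistical Analysis that EF is a continuous outcome, analysed by linear regression of follow-up EF on group and pre-treatment EF, with the adjusted mean difference and 95% CI reported. Include pre-treatment EF as a covariate in the EF equation of the mediation model. In endpoint 5, name EF as the parameter, and state which scan supplies the pre-treatment value and when the follow-up scan is taken.

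The cost is this short addition and about one degree of freedom. No scan is needed beyond the starting one that improvement already requires, although the protocol must say when that scan is done. If the data have already been unblinded, report the adjusted analysis as post hoc.

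### Do the two sample-size statements, 25 per arm (50 in total) and 35 per arm (70 in total), conflict in a way that undermines the trial's power?

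*Combined protocol and SAP*

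**What the plan says.** The sample size is described twice.

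- **Methodology, Sample Size.** At 80% power and alpha 0.05, a "sample size of 25 patients per group total 50 patients can detect an effect size .80". The sentence then runs on to "the difference between two groups regarding different qualitative outcome measures using two-sized a z test".
- **Sample Size Calculation (after the ethics text).** The calculation is for "detecting an effect size of 0.80 in GCS change", with the same alpha, power and 25 per arm. No test is named for it. The section goes on: "To ensure adequate power for secondary endpoints and allow for dropouts, we enrolled 35 patients per group", which makes 70 in total.

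Three other places bear on the point:

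- The primary end point is "Improvement of Glasgow coma scale and spontaneous breathing trial before ICU discharge", and five secondary end points follow it.
- Under Statistical Analysis, the primary analysis is: "Linear mixed-effects regression modeled GCS trajectories over time".
- The same section compares continuous variables by Student's "t-test or Mann-Whitney U test, as appropriate", and sets all tests as two-tailed.

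**The concern.** Both descriptions stand as current text, and neither is marked as replaced. Read side by side, they raise three doubts.

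1. **What was powered.** One description speaks of qualitative outcomes and a z test, the other of GCS change. If 0.80 were a difference between proportions on the arcsine scale (Cohen's h), it would be a different clinical claim from a mean difference of 0.8 SD, and its plausibility would have to be judged differently.
2. **Why 50 became 70.** The increase is 20/50 = 40%, with no date, assumed dropout rate or calculation. If it had been decided after outcomes by arm were known, the type I error could be affected.
3. **The claim about secondary endpoints.** No target difference, SD, event rate or power is given for any of the five. A reader might take a non-significant secondary result as coming from a comparison known to be well powered.

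**Working it through.** **Inputs.** Two-sided alpha 0.05, power 80%, effect size 0.80 and 25 per arm appear in the documents, as does 35 per arm enrolled. The dropout rates below are assumptions, because the documents give none.

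**Step 1: reproduce the plan's 25.** For a standardised mean difference d, the normal approximation gives

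n per arm = 2(z₀.₉₇₅ + z₀.₈₀)² / d² = 2(1.960 + 0.842)² / 0.80² = 15.70 / 0.64 = 24.53, so 25.

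The figure is right for a two-sided z calculation. The exact t-test calculation gives 25.52, so 26. The difference of one patient per arm is immaterial: power at 25 per arm is 80.7% by z and 79.1% by t.

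**Step 2: can the 25 show which outcome was meant?** No. On the arcsine scale each arm's transformed proportion has variance 1/n, so h = 0.80 leads to the same formula and the same 25. With an illustrative control rate of 30%, h = 0.80 corresponds to 30% against 69%. The text has to settle the question, and it does. The later section names GCS change, and the primary analysis treats GCS as continuous in a linear mixed model. Only the garbled earlier sentence points elsewhere.

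**Step 3: what does 35 per arm deliver at 0.80?** By z, power = Φ(0.80·√(n/2) − 1.960).

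- n = 25: Φ(2.828 − 1.960) = Φ(0.868) = 80.7%
- n = 35: Φ(3.347 − 1.960) = Φ(1.387) = 91.7%

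By t test, with dropout assumed at 0%, 10% and 20%:

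| Loss (assumed) | Evaluable per arm | Power at 0.80 |
|---|---|---|
| 0% | 35 | 91.0% |
| 10% | 31 (31.5 rounded down) | 87.3% |
| 20% | 28 | 83.6% |
| 25.7% | 26 | 80.7% |

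The tolerable loss is 1 − 26/35 = 25.7% by t, or 1 − 25/35 = 28.6% by z.

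**Step 4: the secondary endpoints.** The smallest difference detectable with 80% power by two-sided t test at 0.05 is 0.68 SD with 35 per arm and 0.81 SD with 25 evaluable per arm. If Mann-Whitney is used on normal data (an assumption; efficiency 0.955), these become about 0.70 and 0.83 SD. At 35 per arm, an assumed 0.5 SD has 54% power and 0.6 SD has 70%. Whether this is adequate depends on target differences that the documents do not state. Every evaluable patient contributes to every endpoint, so allowing for dropout does not use up a separate reserve kept for the secondary comparisons.

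**The case for a change.** The strongest case for a change is that this costs only words. The earlier paragraph still states a total of 50. No stated input leads to 35. The secondary-power phrase asserts something that the documents do not show, and with no loss it would hold only for differences of about 0.68 SD or more. The later section is written in the past tense, and nothing records when the increase was decided.

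Much of this is factually correct. The earlier sentence is unclear and does not match the later one. The increase is explained only in words, and the phrase about secondary endpoints is unsupported.

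What does not stand is the reading of these gaps as a conflict or an error. The later section reconciles 25 and 35 itself and gives two reasons for the difference. It also names the outcome, so a reader can tell what was powered. Late knowledge of outcomes by arm is conjecture: the documents describe no interim look, although they do not rule one out. That the calculation leaves out the spontaneous breathing trial is a matter of how the primary end point is defined, and is separate from whether these sample sizes agree.

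**Conclusion.** No change to the plan follows. The calculated size is correct for a two-sided z calculation. The enrolled size exceeds it, giving about 91% power by t test at 0.80 against the stated 80%, with room for about 26% loss. These figures rest on the plan's effect size of 0.80 and on a two-group comparison; power under the planned mixed model may differ.

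The remaining defects are a garbled sentence, an increase without a date or dropout rate, and a remark on secondary power that is unsupported but not shown to be false. Correcting them would document or reword what is there. It would alter no analysis, no result and no number shown to be wrong. An analyst would take the later section as the operative one: GCS change as the sizing outcome, 25 per arm required, 35 per arm enrolled. A reader of the secondary results should rely on their confidence intervals and not on the phrase about adequate power.

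### Ventilation time, ICU stay and hospital stay are not assigned to a method, and no rule covers patients who die before extubation or discharge

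*Combined protocol and SAP*

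**What the plan says.** Under Endpoints of the study, three of the five secondary endpoints are durations, given by name only: "Total ventilation time", "Total ICU stay" and the length of hospital stay. None has a stated starting point, terminating event or analysis scale.

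Statistical Analysis contains two generic lines that could each cover them. Continuous variables are compared by "t-test or Mann-Whitney U test, as appropriate". For time-to-event outcomes, "Kaplan-Meier curves and Cox proportional hazards models yielded hazard ratios (HRs) and 95% confidence intervals (CIs". Neither line lists its outcomes, and the second gives no origin, event or censoring rule.

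The same section states "Analyses adhered to the intention-to-treat principle". That fixes who is analysed, not what value a patient who dies receives. The plan has no mortality endpoint, competing-risk rule, worst-rank rule or survivors-only rule.

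Under Anesthetic management, delayed recovery is "prolonged ventilation for 48 hours or delayed conscious level recovery for 48 hours", and follow-up is described as "Daily assessment of conscious level according to Glasgow Coma Scale (GCS) and spontaneous breathing trial by ICU consultant till ICU discharge". Death in the ICU is not mentioned.

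**The concern.** The population is aged 45 to 70, includes emergency open-heart surgery, and has not recovered at 48 hours. Some deaths before extubation or discharge are plausible, and they end all three clocks. What a death does to the result depends on a choice the plan leaves open.

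- **Raw days in all randomised patients.** A death on day 3 enters as a three-day stay, the same as a fast recovery. The arm with more deaths looks faster, and a treatment that both speeds recovery and prevents deaths loses part of its apparent benefit.
- **Kaplan-Meier with deaths censored.** One minus the curve estimates recovery as if nobody could die, so it exceeds the proportion actually extubated or discharged.
- **Cox with deaths censored.** This estimates the cause-specific hazard ratio and is close to unaffected.

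Because no outcome is assigned to a line, the route can be chosen after the data are seen. The secondary endpoints also carry weight in the design. Under Sample Size Calculation, the plan says: "To ensure adequate power for secondary endpoints and allow for dropouts, we enrolled 35 patients per group".

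**Working it through.** **The plan's own figure.** For effect size 0.80, two-sided 0.05 and 80% power: n = 2(1.960 + 0.842)²/0.80² = 24.5, so 25 per arm, as stated. With 35 per arm the power for that effect is 91.7% (normal approximation). This point does not dispute the sample size.

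**Inputs.** From the documents: 35 per arm, two-sided 0.05. Assumed, because the documents give no rates: exponential extubation times at rate λ = 0.15/day (range 0.08 to 0.25), and a proportion p dying before extubation, which gives a death hazard μ = λp/(1−p).

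**1. Raw mean duration.** Mean = 1/(λ+μ) = (1−p)/λ. At p = 10% it is 0.90/0.15 = 6.00 days. At p = 20% it is 0.80/0.15 = 5.33 days. Ten more points of deaths remove 0.67 day with recovery speed unchanged (0.10/0.25 = 0.4 day to 0.10/0.08 = 1.25 days over the range).

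**2. One minus Kaplan-Meier against true cumulative incidence at day 28.**
Incidence = λ/(λ+μ) × [1 − exp(−28(λ+μ))]. One minus KM = 1 − exp(−28λ) = 1 − exp(−4.2) = 0.985.
Worked at p = 10%: μ = 0.0167, λ+μ = 0.1667, incidence = 0.90 × (1 − exp(−4.667)) = 0.892.

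| Deaths | Incidence | 1−KM | Excess, points | Excess for λ = 0.08 to 0.25 |
|---|---|---|---|---|
| 2% | 0.967 | 0.985 | 1.8 | 1.3–2.0 |
| 5% | 0.939 | 0.985 | 4.6 | 3.3–5.0 |
| 10% | 0.892 | 0.985 | 9.3 | 6.8–9.9 |
| 20% | 0.796 | 0.985 | 18.9 | 14.2–19.9 |

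**3. False result in favour of the higher-death arm.** Equal recovery speed, 35 per arm, 20,000 simulated trials per row, nominal 2.5%. The log-rank test with deaths censored stands for the Cox score test.

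| Deaths by arm | Mann-Whitney | t-test | Log-rank |
|---|---|---|---|
| equal (2%, 5% or 10%) | 2.4–2.5% | 2.3–2.5% | 2.7–2.8% |
| 2% v 5% | 3.2% | 3.3% | 2.8% |
| 5% v 10% | 3.8% | 3.9% | 2.7% |
| 10% v 20% | 6.1% | 6.6% | 2.7% |
| 10% v 30% (extreme) | 14.0% | 16.3% | 2.8% |

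Log-normal extubation times (log SD 0.8) give a similar picture: 6.8%, 6.8% and 2.7% at 10% v 20%.

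**4. Where Cox is not fully protected.** If deaths fall only on slow recoverers (half the patients at 0.08/day, half at 0.30/day), the log-rank rate is 3.2% at 5% v 10%, 3.9% at 10% v 20% and 6.2% at 10% v 30%.

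**5. Hidden benefit.** Extubation rate doubled and death hazard halved. Power by control-arm deaths:

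| Control deaths | Mann-Whitney | t-test | Log-rank |
|---|---|---|---|
| none | 69% | 79% | 80% |
| 10% | 58% | 69% | 78% |
| 20% | 47% | 56% | 75% |

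The effect of deaths is the fall down each column. From none to 10% it is about 11 points for Mann-Whitney, 10 for the t-test and 2 for the log-rank test.

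**The case against.** The strongest reply is that the plan already holds the remedy. It has a Kaplan-Meier and Cox line, the three durations are the obvious candidates for it, and no mortality endpoint competes for it. On that reading the hazard ratio is nearly unaffected and only the recovery percentages are too high. Much of this stands, and it is why the fix keeps the plan's own model. It does not close the gap. Time to improvement in consciousness or to a successful breathing trial could equally be what that line means, and the continuous-variable line remains available.

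Several stronger readings are tempting but are not supported:

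- **That the trial will test raw days, or that its result will be biased.** The documents do not say which test is used. Inflation also needs unequal deaths, and no death rate is given, so no row of the table can be called likely.
- **That the Cox model is invalid because death competes.** It remains a sound cause-specific comparison except when deaths concentrate on slow recoverers.
- **That the whole power gap comes from deaths.** At 10% control deaths, Mann-Whitney trails log-rank by 20 points (58% v 78%), but 11 of those exist with no deaths, because exponential times favour log-rank. With log-normal times and no deaths the order reverses (73% v 68%).
- **That patients already extubated at entry are mishandled.** The entry definition allows them, but each has a definite total ventilation time. A difficulty arises only if the clock is moved to randomisation.

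It is also fair that choosing cause-specific Cox over a worst-rank test is partly preference, because the two answer different questions.

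**Conclusion.** The point stands as a gap with a conditional consequence. The plan permits two routes for three secondary endpoints and gives no rule for death on either. On raw days, an imbalance in deaths distorts the comparison: no inflation with equal deaths, about one point at 5% v 10%, and about four points at 10% v 20%, against a nominal 2.5%. On Kaplan-Meier with deaths censored, recovery at day 28 is overstated by about 9 points at 10% deaths and 0.15/day, while the hazard ratio is nearly right. These sizes rest on assumed death and extubation rates, and on independent exponential times unless stated otherwise. A reader might infer that the main conclusion or the sample size is undermined. Neither is: the primary analysis is a mixed model of the Glasgow Coma Scale, and the 25 per arm reproduces.

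**What to change.** In the SAP:

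1. Assign the three durations to the existing time-to-event line. Define the events as extubation alive, ICU discharge alive and hospital discharge alive, and state the time origin. The extubation definition should say how re-intubation, and death after extubation, are classified.
2. Keep the plan's Cox model as the single comparison for each, read as a cause-specific hazard ratio with deaths censored at death.
3. Replace one minus Kaplan-Meier with Aalen-Johansen cumulative incidence by arm, with death as the competing event.
4. Do not test raw days in all randomised patients.
5. Report counts of in-hospital deaths by arm beside each result. A hazard ratio for death is not needed: with 35 per arm, the chance that at least one arm has no deaths is 1 − (1 − 0.98³⁵)² = 74% at 2% mortality and 1 − (1 − 0.95³⁵)² = 30% at 5%.
6. If ventilation is timed from randomisation, report by arm how many were already extubated and state how they are handled, consistently with the intention-to-treat statement.
7. A worst-rank Mann-Whitney may be added as an optional sensitivity analysis, labelled as mixing survival with speed.

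The cost is SAP wording and standard R software, plus confirmation that dates of extubation, ICU discharge, hospital discharge and in-hospital death are recorded. Recovery percentages will look lower than Kaplan-Meier would show, and the Cox result must be read beside the deaths. The statistical section is written in the past tense, so if analysis has begun the change must be labelled post hoc.
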